4.03. Safety analyses of the safety endpoints will be performed based on the Safety Analysis Set (consisting of all subjects who are randomized and receive any investigational product post randomization) according to the actual treatment received. Treatment-emergent adverse events post randomization are defined as adverse events that start or worsen on or after the first dose of investigational product post randomization and prior to the EOS. The numbers and percentages of subjects reporting treatment-emergent adverse events, serious adverse events and events of interests will be tabulated by treatment group. The number and percent of subjects developing binding or neutralizing antidrug antibodies (ADA) in the subset of Safety Analysis Set who have never tested positive (ie, tested negative or no results) prior to the first dose of investigational product post randomization and have at least one ADA result post randomization will be tabulated descriptively by treatment group and by visit.

In addition, safety analyses prior to randomization will be performed based on the Lead-in Treated Set (consisting of all enrolled subjects treated with at least 1 dose of investigational product during the lead-in period). The number and percentage of subjects reporting treatment-emergent adverse events, serious adverse events and events of interest while receiving adalimumab during the lead-in period will be summarized. The number and percentage of subjects developing binding or neutralizing ADAs for adalimumab during the lead-in period will be summarized.

Clinical Study Protocol: 20200497 Final 1.0 Date: 03 Jun 2021

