4.2 Scientific Rationale for Study Design

The current study is designed to demonstrate that the risk in terms of safety or diminished efficacy of switching between ABP 501 (a proposed interchangeable biosimilar product) and adalimumab (a reference product) is not greater than the risk of using adalimumab without such switch.

A dedicated switching study approach has been selected, as outlined in the US FDA guidance (Guidance for Industry: Biosimilars: Considerations in Demonstrating Interchangeability with a Reference Product, May 2019).

This study is designed to assess whether switching between adalimumab (reference product) and ABP 501-HCF (three switches with the last switch from adalimumab to ABP 501-HCF) will result in differences in PK or immunogenicity profiles, when compared to continued therapy with adalimumab (reference product). The C_{max} and AUC_{tau} at the end of multiple switching between investigational products were chosen as co-primary PK study endpoints.

The FDA guidance provides recommendations to conduct clinical switching studies in relevant patient population rather than in healthy volunteers. Population of subjects with moderate to severe plaque psoriasis was thus selected for this study, as it offers a sensitive model to detect potential differences with regard to immunogenicity, PK, safety, and efficacy (Guidance for Industry: Biosimilars: Considerations in Demonstrating Interchangeability with a Reference Product, May 2019) in a repeat dose setting.

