9.5.3 Safety Endpoints

All reported adverse events will be categorized by system organ class and preferred term according to the Medical Dictionary for Regulatory Activities (latest version at the time of final analysis) dictionary and graded by CTCAE, version 4.03.

Safety analyses of the safety endpoints will be performed based on the Safety Analysis Set according to the actual treatment groups (switching group versus continued-use group). Treatment-emergent adverse events post randomization are defined as adverse events that start or worsen on or after the first dose of investigational product post randomization and prior to the EOS. The numbers and percentages of subjects reporting treatment-emergent adverse events, serious adverse events and events of interests will be tabulated by treatment group. The number and percent of subjects developing binding or neutralizing antidrug antibody (ADA) in the subset of Safety Analysis Set who have at least one ADA result post randomization will be tabulated descriptively by treatment group and by visit.

Laboratory data (hematology, serum chemistry, and urinalysis) will be converted to Système International units for reporting purposes. Absolute values and changes from week 12 for laboratory data post randomization will be summarized descriptively by treatment group and visit.

For vital signs post randomization, absolute values, and changes from week 12 will be summarized descriptively by treatment group and visit.

Physical examination values post randomization will be summarized descriptively by treatment group and by visit.

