Developing antibody incidence during the Post-randomization Period is defined as the number of subjects in the Safety Analysis Set (SAS) who have a positive result post randomization and have never tested positive (i.e., negative or no results) prior to the first dose of post-randomization IP divided by the number of subjects in the SAS who have at least a result post randomization.

End of Study (EOS) Date

The EOS date is the date recorded on the End of Study page of the CRF.

First Dose Date

It is defined as the date the subject received the first dose of IP.

First Post-randomization Dose Date

It is defined as the date the subject received the first post-randomization dose of IP.

Last Dose Date

It is defined as the date the subject received the last dose of IP.

Last Observation Carried Forward (LOCF)

Protocol Number: 20200497

Date: 10FEB2023 Page 14 of 36

A method of imputation where missing post-baseline data will be imputed by carrying forward the last non-missing post-baseline value for that endpoint. Baseline values will not be carried forward.

Neutralizing ADA Negative Subgroup

Defined as subjects in the subset of Safety Analysis Set (SAS) who have never tested positive (i.e. tested negative or no results) prior to the first dose of post-randomization IP, have at least one neutralizing ADA result post-randomization, and all available post-randomization neutralizing ADA results are negative.

Non Responder Imputation (NRI)

A method of imputation where a subject with missing post-baseline binary response data will be imputed as a non-responder, regardless of the reasons for missing data.

Study Analysis Visit

If more than one actual visit (including the unscheduled visits) falls within the same defined window, the visit closest to the target day with non-missing data will be considered for analysis. If two actual visit dates are at the same distance from the target day, the later visit with non-missing data will be considered for analysis.

For Efficacy, Vital, Safety Lab & PK

					Endpoint	
Study Analysis Visit	Target Day	Study Day	Interval (days)	Efficacy	Vital & Safety Labª	PK
Baseline ^b	1	≤1	NA	Х	Х	Х
Week 2	8	2-21	20		X	
Week 6	36	22-56	35	Χ	X	Χ
Week 12 ^b	78	57-91	35	Χ	X	Χ
Week 16	106	92-119	28	Χ	X	Χ
Week 20	134	120-161	42	Χ	X	Χ
Week 28	190	162-196	35		X	Χ
Week 30	14 days post week 28 dose	197-210	14	Х	Х	
Week 32	218	≥211	NA		Χ	

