for subjects who are randomized and treated post-randomization, or to the EOS visit for

subjects not randomized or for subjects who were randomized but not treated post-

randomization.

Post-randomization Period

For subjects who are randomized and treated post-randomization, it is defined as the

time period from the first post-randomization dose to the EOS visit.

Study Randomization

Study randomization is defined as when subject receives a random treatment allocation

via the IXRS system.

Total IP Exposure Duration

The total IP exposure duration for the subject (in weeks) for each study period (Lead-in

Period, Post-randomization Period) will be derived as: (the period end date - the period

start date+1)/7. The Lead-in Period end date for the subjects who are randomized and

treated post-randomization is the date of the first IP post randomization -1.

Transient ADA

A transient ADA result during the Lead-in Period is defined as a positive antibody result

post-baseline (including unscheduled visits) during the Lead-in Period with a negative or

no antibody result at baseline and a negative result at the subject's last visit tested within

the Lead-in Period.

Protocol Number: 20200497

Date: 10FEB2023 Page 17 of 36

A transient ADA result during the Post-randomization Period is defined as a positive antibody result post-randomization (including unscheduled visits) during the Post-randomization Period with negative or no antibody results prior to the first dose of post-randomization IP and a negative result at the subject's last visit tested within the Post-randomization Period.

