9.7.6 Antibody Formation

The number and percent of subjects developing binding or neutralizing ADA will be tabulated descriptively by treatment group and visit in the SAS for the Postrandomization Period and in the LTS for the Lead-in Period.

The incidence of transient antibody will also be summarized for each study period.

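### The post-randomization ADA tables cannot count anyone already positive in the lead-in, and the SAP does not say whether that rule applies per assay

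*SAP*

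**What the plan says.** Every subject receives six adalimumab doses before randomization at week 12. ADA is sampled at baseline and weeks 6 and 12, then at weeks 16, 20, 28, 30 and 32 (Protocol Table 1-1), before dosing at dosing visits.

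SAP 5.1 defines developing ADA after randomization. The numerator is subjects with a positive result in that period who "have never tested positive (i.e., negative or no results) prior to the first dose of post-randomization IP". This count is "divided by the number of subjects in the SAS who have at least a result post randomization". Transient ADA is a post-randomization positive "with negative or no antibody results prior to the first dose of post-randomization IP and a negative result at the subject's last visit" tested in the period. Neither definition says whether a positive means any antibody or the antibody being tabulated.

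SAP 9.7.6 then states: "The number and percent of subjects developing binding or neutralizing ADA will be tabulated descriptively by treatment group and visit in the SAS" for this period. It adds the incidence of transient antibody and nothing else.

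The protocol gives two populations. The synopsis uses Safety Analysis Set subjects "who have never tested positive (ie, tested negative or no results) prior to the first dose of investigational product post randomization" who also have a later result, as one subset for binding and neutralizing ADA together. Section 9.5.3 places the count "in the subset of Safety Analysis Set who have at least one ADA result post randomization will be tabulated descriptively", with no condition on earlier results. The endpoint in Protocol Table 3-1 is ADA incidence after randomization, unqualified. SAP section 10 records a change to the PK analysis sets but none to the ADA definition.

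**The concern.** Protocol 4.2 says the trial is to show whether switching alters immunogenicity as well as PK, relative to staying on adalimumab. Subjects already sensitized by the lead-in are central to that question. Under the SAP definitions they are identified at week 6 or 12 and then cannot contribute a post-randomization ADA event in the assay in which they were positive. If switching boosted or changed antibody responses mainly in this group, the planned ADA comparison could look the same in both arms.

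There is also a specification problem. The rule names no assay, so two programmers could follow SAP 5.1 and produce different neutralizing rows. In addition, the SAP's numerator and denominator describe different groups: prior positives cannot be cases but still count as subjects at risk.

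**Working it through.** The plan states no ADA rate, margin or power, so it has no figure of its own to reproduce. The only sizing input is 342 randomized 1:1 (Protocol 9.3), or 342 / 2 = 171 per arm. All ADA rates below are assumptions.

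**1. Who can be a case of developing ADA**

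| Lead-in result | Post-randomization result | Any-antibody rule | Per-assay rule |
|---|---|---|---|
| Never positive | Positive | Case | Case |
| Positive week 6, negative week 12 | Positive week 16, same assay | Not a case | Not a case |
| Binding-positive, never neutralizing-positive | Neutralizing-positive | Not a case | Case in neutralizing row |
| Neutralizing-positive | Still or again neutralizing-positive | Not a case | Not a case |

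Rows 2 and 4 go uncounted under either reading; row 3 depends on the reading. Transient ADA adds none of them, because it carries the same limit.

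**2. Which reading the text favours.** The synopsis defines a single never-positive subset for both antibody types. In SAP 5.1, the neutralizing-ADA-negative subgroup leaves the antibody unnamed in its pre-dose condition but names neutralizing results in its post-randomization condition. Both point to any antibody. Neither settles it.

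**3. How many subjects.** If 20-60% are positive before the first post-randomization dose: 171 × 0.20 = 34 and 171 × 0.60 = 103 per arm cannot be cases (any-antibody rule).

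**4. Illustration of conversion.** Assume 30% per arm are lead-in binding-positive (51 subjects, leaving 120 never positive). Assume 5% of never-positives become neutralizing-positive in both arms, and that binding-positives convert in 10% on continued use and 40% after switching.
- Continued use: 0.05 × 120 + 0.10 × 51 = 6.0 + 5.1 = 11.1; 11.1 / 171 = 6.5%.
- Switching: 6.0 + 0.40 × 51 = 6.0 + 20.4 = 26.4; 26.4 / 171 = 15.4%.
- Difference: 15.3 / 171 = 8.9 points.
- SAP incidence, any-antibody rule: 6.0 / 171 = 3.5% in both arms, difference 0.
- SAP incidence, per-assay rule: the full 8.9 points appear in the neutralizing row.

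With 10% lead-in binding-positive (17 subjects) the difference is 0.30 × 17 / 171 = 3.0 points; with 50% (86 subjects) it is 0.30 × 86 / 171 = 15.1 points. The any-antibody rule again shows 0.

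These are upper bounds at the assumed conversion rates, because every lead-in binding-positive is treated as neutralizing-negative. If half were already neutralizing-positive, the 8.9 points would fall to 0.5 × 15.3 / 171 = 4.5.

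**5. Denominator.** Assume 20% of never-positives develop ADA. With 10%, 30% or 50% lead-in positive, the SAP rate is 0.20 × 154 / 171 = 18.0%, 0.20 × 120 / 171 = 14.0%, or 0.20 × 85 / 171 = 9.9%. The synopsis denominator gives 20% each time.

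**The case against.** Counting new positives among subjects not positive before the period is a coherent definition of developing ADA. Prior status is fixed before the first post-randomization dose, so the restriction does not by itself bias the comparison between arms. Immunogenicity is a descriptive secondary objective (Protocol 2.1), with no margin or test, so no decision rule changes. All of this stands, and it limits the point to reporting.

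A reader might infer that a switch turning binding-positives into neutralizing-positives would leave no trace in the trial. The documents do not support that. Under a per-assay rule, which SAP 5.1 does not exclude, such subjects are cases in the neutralizing row. The PK Parameter Analysis Set does not exclude ADA-positive subjects, so a response that lowered exposure could show in AUCtau, Cmax or trough. Hypersensitivity and injection site reactions are summarized in the whole Safety Analysis Set. These are indirect routes, though, and do not report antibody status. The neutralizing-ADA-negative PK subgroup requires no earlier positive, so it leaves these subjects out.

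A reader might also infer that prior positives are removed from the analysis. In the SAP they leave only the numerator. They would leave both numerator and denominator only under the synopsis.

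**Conclusion.** The gap is real but confined to the descriptive ADA tables. A subject positive in the lead-in cannot become a developing or transient case in the same assay after randomization, and no other SAP table reports post-randomization ADA for such subjects. Under the any-antibody reading, which the synopsis favours, neutralizing conversion in lead-in binding-positives is also unreported. This is narrower than the protocol endpoint and section 9.5.3, and SAP section 10 does not record the narrowing.

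The structural result needs no assumed rate. Its size does: 34-103 of about 171 per arm rests on an assumed 20-60% lead-in positivity, and the conversion differences are illustrative upper bounds. The primary PK conclusion and the sample size are unaffected. The change is worth making because it is cheap and addresses a stated purpose of the trial.

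**What to change.** In SAP 5.1, apply the rule on earlier positives separately for binding and neutralizing ADA, in both the developing and transient definitions. Developing neutralizing ADA would then be counted in subjects never neutralizing-positive before the first post-randomization dose, whatever their binding status.

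Reconcile the denominator across SAP 5.1, the synopsis and Protocol 9.5.3, which now disagree. One consistent choice is the never-positive subset with a later result for developing ADA (as in the synopsis), and all Safety Analysis Set subjects with a later result for total positivity (as in 9.5.3). Record the choice in SAP section 10.

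In SAP 9.7.6, add one descriptive table of post-randomization binding and neutralizing positivity by group and visit. It should cover all Safety Analysis Set subjects with a result, split by ADA status before the first post-randomization dose. Include a line for neutralizing conversion among lead-in binding-positive, neutralizing-negative subjects.

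The cost is SAP wording and one table from samples already scheduled, with no change to alpha or sample size. Cells in the previously positive stratum may be small. The neutralizing rows also depend on binding-positive samples being tested further, which Protocol 8.9 leaves optional, so the SAP should state whether all of them are tested.

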8.9 Immunogenicity Assessments

Antibodies (binding and neutralizing) to investigational product will be evaluated in serum samples collected from all subjects. Additionally, serum samples should also be collected at the final visit from subjects who discontinued investigational product or were withdrawn from the study. These samples will be tested by the sponsor or sponsor's designee. Samples should be taken prior to administration of investigational product (predose) on dosing visits. Samples tested positive for binding antibodies may be further assessed for neutralizing antibodies. Additional blood samples may be obtained to rule out ADAs during the study.

The detection and characterization of ADAs will be performed using a validated assay method by the sponsor or under the supervision of the sponsor.

9 Statistical Considerations

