9.5.8 Subgroup Analyses and Covariates

The stratification factors (prior biologic use for psoriasis ["yes" versus "no"] at baseline [week 1], and geographic region) will be included as covariates in the statistical models for the PK and efficacy analyses. In addition, weight and PK trough concentration at the end of the lead-in period (week 12) will be included as covariates in the statistical model for the primary PK endpoints. Baseline PASI score will be included as covariate in the statistical model for the PASI percent improvement efficacy endpoint.

Subgroup analyses will be conducted for PK parameter endpoints for neutralizing ADA negative subgroup from the PK Parameter Analysis Set.

Full details of the subgroup analyses and covariates will be pre-specified in the SAP.

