8.3 Handling of Missing, Below LLOQ and Incomplete Data

Missing PK concentration data and endpoints will not be imputed.

For the purpose of calculating AUC $_{tau}$, concentrations that are below the LLOQ after t_{max} will be excluded; values less than the LLOQ that are encountered prior to t_{max} will be set to zero and included. Individual AUC $_{tau}$ will be flagged if less than 2 post t_{max} concentration values are reported or less than 2 post t_{max} concentration values are above LLOQ.

For summary statistics and linear plots for the PK concentrations, concentration values < LLOQ will be set to zero. For log-linear plots, concentration values below LLOQ will not be displayed.

The handling of missing values for efficacy endpoints are detailed in Section 9.6.

Missing safety and ADA endpoints will not be imputed.

Imputation for Partial or Missing Dates

If dates are missing or incomplete for an AE (including deaths) or concomitant medication, the following algorithm will be used for imputation:

Stop Date	
	Stop Date

Protocol Number: 20200497

Date: 10FEB2023 Page 23 of 36

		Complete: yyyymmdd		Partial: yyyymm		Partial: yyyy		Missin g
		<1st dose	≥1st dose	<1st dose yyyym m	≥1st dose yyyymm	<1st dose yyyy	≥1st dose yyyy	
Partial: yyyym m	= 1st dose yyyymm	2	1	n/a	1	n/a	1	1
	≠ 1st dose yyyymm		2	2	2	2	2	2
Partial: yyyy	= 1st dose yyyy	- 3	1	3	1	n/a	1	1
	≠ 1st dose yyyy		3	Č	3	3	3	3
Missing		4	1	4	1	4	1	1

- 1 = Impute as the date of first dose
- 2 = Impute as the first of the month
- 3 = Impute as January 1 of the year
- 4 = Impute as January 1 of the stop year

Note: If the start date imputation leads to a start date that is after the stop date, then there is a data error and do not impute the start date.

Imputation rules for partial or missing stop dates:

- 1. Initial imputation
 - a. For partial stop date "mmyyyy", impute the last of the month.
 - b. For partial stop date "yyyy", impute December 31 of the year.
 - c. For completely missing stop date, do not impute.
- 2. If the stop date imputation leads to a stop date that is after the death date, then impute the stop date as the death date.
- 3. If the stop date imputation leads to a stop date that is before the start date, then there is a data error and do not impute the stop date.

Imputation rules for partial or missing death dates:

- 1. If death year and month are available but day is missing:

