9.5.4 Subgroup Analyses

The primary PK endpoints will be summarized and compared within the neutralizing ADA negative subgroup for the PK Parameter Analysis Set and employing the analysis methods described in Section 9.5.1.1.

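### SAP 5.1 requires a neutralizing ADA result for the neutralizing ADA negative PK subgroup; with the tiered testing in Protocol 8.9, this literally excludes subjects who never formed antibody

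*SAP*

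**What the plan says.** Protocol 9.5.8 plans the subgroup and leaves its details to the SAP: "Subgroup analyses will be conducted for PK parameter endpoints for neutralizing ADA negative subgroup from the PK Parameter Analysis Set". SAP 9.5.4 says how it is used: "The primary PK endpoints will be summarized and compared within the neutralizing ADA negative subgroup for the PK Parameter Analysis Set", with the methods of SAP 9.5.1.1. That means the log-scale ANCOVA adjusted for stratification factors, weight and week 12 trough, with 90% confidence intervals for the geometric mean ratio (GMR).

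SAP 5.1 defines membership within the Safety Analysis Set by three conditions. The first limits it to subjects "who have never tested positive (i.e. tested negative or no results) prior to the first dose of post-randomization IP"; no assay is named. The second and third require that they "have at least one neutralizing ADA result post-randomization, and all available post-randomization neutralizing ADA results are negative".

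Protocol 8.9 covers the testing. It opens generally: "Antibodies (binding and neutralizing) to investigational product will be evaluated in serum samples collected from all subjects". It then gives the sequence: "Samples tested positive for binding antibodies may be further assessed for neutralizing antibodies". On absent results, SAP 8.3 says: "Missing safety and ADA endpoints will not be imputed".

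**The concern.** A reader expects a neutralizing ADA negative group to consist largely of subjects who never made antibody. Under tiered testing those subjects have no neutralizing result, so the requirement for at least one removes them. What remains is a group selected mainly for having become binding-positive, close to the reverse of the label.

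This is the only planned subgroup analysis. Its natural purpose is to show whether exposure is similar once clearance by neutralizing antibody is set aside. In the wrong population it cannot show that. If programmers instead treat binding-negative samples as neutralizing-negative without a written rule, the analysis is sensible but its population has not been pre-specified.

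**Working it through.** **The plan's own figure.** SAP 3.2 gives 342 randomized 1:1, 15% dropout, CV 53%, true GMR 1, margin 0.8 to 1.25, two one-sided tests at 0.05, and at least 90% power.

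- Log-scale SD: σ = √ln(1 + 0.53²) = 0.4976.
- Evaluable: 342 × 0.85 = 290.7, or about 145 per arm.
- Power per endpoint, normal approximation: 2Φ(ln 1.25 / (σ√(2/145)) − 1.645) − 1 = 97.0%. The exact t calculation also gives 97.0%.
- Both endpoints together: at least 2 × 0.9696 − 1 = 93.9%.

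The whole-study claim is met. No size or power is stated for the subgroup.

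**The definition, traced by type of subject.** Take subjects with no positive test before the first post-randomization dose, and tiered testing as in Protocol 8.9.

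| Post-randomization samples | Neutralizing result exists? | In subgroup, read literally? |
|---|---|---|
| All binding-negative | No | No |
| Binding-positive, not sent on | No | No |
| Binding-positive, all neutralizing results negative | Yes | Yes |
| Binding-positive, any neutralizing result positive | Yes | No |

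Only the third row qualifies. If the unnamed assay in the first condition is the neutralizing one, subjects who were binding-positive but not neutralizing-positive during the lead-in can also qualify. Subjects who never formed antibody are excluded on either reading.

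**Size.** The documents give no ADA rates, so these are assumptions: of 290 evaluable subjects, a proportion L of 0 to 40% already positive before the first post-randomization dose (any assay), B of 10 to 40% of the rest newly binding-positive, and q of 10 to 30% of those neutralizing-positive. All binding-positive samples are assumed to be sent on.

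- Literal total = 290 × (1 − L) × B × (1 − q)
- Intended total = 290 × (1 − L) × (1 − B × q)

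Example with L = 20%, B = 20%, q = 10%: literal 232 × 0.2 × 0.9 = 42; intended 232 × 0.98 = 227.

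| L, B, q | Literal total (power) | Intended total (power) | Share kept |
|---|---|---|---|
| 20%, 20%, 10% | 42 (1%) | 227 (92%) | 18% |
| 0%, 40%, 10% | 104 (47%) | 278 (96%) | 38% |
| 0%, 10%, 10% | 26 (0.1%) | 287 (97%) | 9% |
| 40%, 10%, 30% | 12 (0%) | 169 (79%) | 7% |
| 40%, 40%, 30% | 49 (2%) | 153 (74%) | 32% |

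Power is for one endpoint, unadjusted, at CV 53% and true GMR 1.

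**Width of the interval.** The half-width on the log scale is t(0.95, 2n − 2) × σ × √(2/n), to be compared with ln 1.25 = 0.223. At an observed GMR of 1 and without adjustment:

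- 17 per arm: 0.289, interval 0.75 to 1.34.
- 26 per arm: 0.231, interval 0.79 to 1.26.
- 83 per arm: 0.128, interval 0.88 to 1.14.

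The planned model is adjusted. If the covariates explained 30% of log variance (assumption), σ falls to 0.4976 × √0.70 = 0.416, and 26 per arm gives 0.82 to 1.21. If they explained 45% (assumption), σ falls to 0.369, and 17 per arm gives 0.81 to 1.24. Both lie inside the margin. These ignore the few degrees of freedom spent on covariates.

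**The case against.** The strongest reply is that Protocol 8.9 never restricts neutralizing testing to binding-positive samples. Its tiering sentence is permissive, and the paragraph opens by promising both kinds of antibody evaluation in all subjects' samples. Reporting of a binding-negative sample is a matter for the laboratory data specification, which is not among the documents. If such samples arrive coded as neutralizing-negative, the SAP definition works as written. The SAP 8.3 rule against imputation does not clearly settle this, because a sample tested and found binding-negative is not plainly missing.

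This stands as a limit on the practical consequence, not on the defect. The convention that would rescue the definition is unwritten, and the SAP is where Protocol 9.5.8 says it belongs. The wording points to a slip: for post-randomization ADA incidence, the protocol synopsis uses nearly the same subset but asks only for an ADA result, without specifying neutralizing.

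It can also be said that any subgroup based on post-randomization neutralizing status, including the repaired one, conditions on a post-randomization event. That is true. The repair restores the intended population and does not turn the comparison into a fully randomized one.

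**Conclusion.** The rule as written is wrong for its label. Read with Protocol 8.9, it excludes subjects who never formed antibody and keeps mainly binding-positive, neutralizing-negative ones, unless an unstated laboratory convention intervenes. Under the assumed ADA rates it keeps about 7% to 38% of the intended subjects: 12 to 104 in total against 153 to 287. Another assumed set (20 to 60% positive beforehand, 15 to 30% newly binding-positive, 20 to 40% of those neutralizing) gives about 5 to 28 per arm against 51 to 113. The direction is firm; the size depends on rates that the documents do not give.

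Three stronger readings are not supported:

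- A reader might infer that a subgroup of 26 or fewer per arm must miss 0.8 to 1.25 even for identical products. That holds only for an unadjusted analysis at CV 53% and observed GMR 1; the plan specifies a covariate-adjusted model.
- A reader might infer that only newly binding-positive subjects remain. The first condition names no assay, and newly positive subjects who are neutralizing-positive are removed.
- A reader might infer a threat to the trial's conclusion. Success rests on the primary analysis of AUCtau and Cmax alone (Protocol 9.2, SAP 2.2), and the subgroup has no part in it.

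The correction should be made, but it is not critical to the trial.

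**What to change.** Rewrite the subgroup definition in SAP 5.1 before unblinding so that it:

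1. requires at least one binding ADA result after randomization and no post-randomization sample positive for neutralizing ADA;
2. states that a sample negative for binding ADA counts as negative for neutralizing ADA;
3. names the assay, binding or neutralizing, meant by the condition of no positive test before the first post-randomization dose.

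The cost is a sentence or two in the SAP and the matching derivation in the analysis datasets. No new samples or assays are needed. Protocol 8.9 can stay as it is: making neutralizing testing of binding-positive samples mandatory would address a separate question, and admitting the never-antibody subjects does not depend on it.
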